The primary goal of this proposal is to determine the efficacy of tranexamic acid in reducing the rate of hematoma formation after breast reduction surgery. This will be a double-blinded, randomized controlled study. The research will be achieved by randomizing one breast in a bilateral breast reduction to receive topical tranexamic acid, while the other breast will not receive the study drug. Both the surgical team and the patient will be blinded to which side has received the study drug. The patient will then be followed for the standard postoperative period and the rate of hematoma development will be recorded. Patient demographics, comorbidities, treatment history, and surgical details will be collected from these charts and analyzed for their impact on perioperative blood loss. **We hypothesize that use of topical tranexamic acid will decrease the rate of hematoma formation and the rate of blood transfusion without increasing the incidence of deep vein thrombosis or thromboembolic events.**

b) Target Population and Recruitment Methods

Consecutive patients presenting for breast reduction mammoplasty performed by plastic surgeons affiliated with Montefiore Medical Center will be offered enrollment in the study. Potential study participants will be recruited at their preoperative consultation appointments that take place at the Hutchinson Metro Center campus. Written informed consent (detailed below) will be obtained from all participants before inclusion. As this proposal involves greater than minimal risk to patients, we will have a Data and Safety Monitoring Plan in place prior to beginning the study.

c) Inclusion and Exclusion Criteria

Inclusion criteria include: being over the age of 18 and being scheduled for reduction mammoplasty at the Hutchinson Metro Center campus of Montefiore Medical Center.

Exclusion criteria include: oncologic breast reductions, unilateral breast reductions, history of thromboembolic disease, history of bleeding diatheses, history of stroke, current pregnancy, severe comorbidity (defined as American Society of Anesthesiologists (ASA) fitness grade IV or above).

d) Primary and Secondary Outcomes

Primary outcome: development of hematoma within 30 days of surgery

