Rationale: Topical tranexamic acid has been shown to reduce perioperative blood loss and need for transfusion. A recent randomized controlled trial showed that topical tranexamic acid significantly decreased 24-hour drain output following reduction mammoplasty, though the clinical significance of this was unclear.

- *We hypothesize that breasts treated with topical tranexamic acid will have a lower rate of hematoma development compared to the contralateral control.*

Secondary outcome: incidence of blood transfusion within 30 days of surgery, incidence of deep vein thrombosis, and incidence of pulmonary embolism

Rationale: Tranexamic acid is an antifibrinolytic, and therefore acts by inhibiting fibrinolysis and stabilizing clot formation. There has historically been concern that

use of tranexamic acid will increase the incidence of thromboembolic events such as deep venous thrombosis and pulmonary embolism.

- *We hypothesize that patients treated with topical tranexamic acid will not have an increased rate of thromboembolic events compared to nationally published rates and those of our own historical controls.*

e) Study Timelines

We anticipate that data collection from the treatment arm will take 8 months and analysis and manuscript preparation will take another 4 months.

4) Study Population

a) Study Population

The study population will comprise all patients over the age of 18 scheduled to undergo breast reduction surgery at the Hutchinson Medical Center campus of Montefiore Medical Center, who meet the inclusion and exclusion criteria outlined above. No patients from before the beginning of electronic medical record use at Montefiore Medical Center will be used, as it will not be possible to explore these patients' medical records. As this proposal involves greater than minimal risk to patients, we will have a Data and Safety Monitoring Plan in place prior to beginning the study.

b) Vulnerable Populations

Include	Exclude	Vulnerable Population Type
	X	Adults unable to consent
	X	Individuals who are not yet adults (e.g., infants, children, teenagers)
	X	Wards of the State (e.g., foster children)
	X	Pregnant women
	X	Prisoners

c) Informed Consent Process

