We will be requesting a waiver of consent and HIPAA authorization for recruitment purposes (so as to find eligible participants for the study), but we are not seeking a waiver for the study as a whole as we are obtaining informed consent from the study participants.

e) Economic Impact on Subjects

None

7. Protocol Methodology

We have based our research strategy on that of the previously published randomized controlled trial performed by Ausen et al.¹⁶ The randomization will be performed electronically by the Albert Einstein College of Medicine Clinical Research Center. Patients will be randomized to receive topical tranexamic acid to one breast and placebo (topical saline) to the other, after obtaining hemostasis but prior to closure

during reduction mammoplasty. The study drug will be prepared and randomized with the assistance of the Einstein Investigational Drug Service as detailed below.

A custom order for the study drug will be created in Epic. Each week, the list of patients scheduled to undergo reduction mammoplasty the following week will be provided to the pharmacy. The Investigational Drug Service at Einstein will prepare randomization kits comprised of two identical 20cc syringes labeled "LEFT" or "RIGHT" based on the existing randomization table. Our pharmacy carries a standard vial of tranexamic acid at a concentration of 100mg/mL, with 10mL per vial (total 1g of TXA). We will dilute the tranexamic acid to a volume capable of moistening the typical wound surface of reduction mammoplasty; 20 mL has been shown to sufficiently moisten at least 1500cm².¹⁶ The side pre-randomized to treatment will contain 10cc of 100mg/mL of tranexamic acid diluted in 10cc of normal saline (0.9% sodium chloride). The other vial will contain 20cc of of normal saline. Tranexamic acid is colorless, therefore the two syringes will appear identical.

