Subject treatment assignments will remain blinded until the final subject has completed follow up and all data has been recorded and validated. Urgent, immediate unblinding due to medical emergency may be authorized by the Investigator. When possible, the treatment assignment will be provided to the treating physician in order to maintain the blind for the Investigator and study staff.

8. Data Analysis

We hypothesize that use of topical tranexamic acid will decrease total perioperative blood loss, hematoma formation, and transfusion rates without increasing the incidence of deep vein thrombosis or thromboembolic events.

a) Chart review data:

Patient charts will be abstracted for baseline demographic data and medical comorbidities that may independently increase the risk of developing a postoperative hematoma. Data to be abstracted from the medical record includes: demographic data (including patient gender, age, ethnicity), medical data (including body mass index, comorbidities (e.g. hypertension, diabetes, hyperlipidemia, coronary artery disease), smoking history, history of neoadjuvant radiation therapy or chemotherapy, history of thromboembolic disease, bleeding diatheses, or use of anticoagulant medications), surgical data (including type of operation performed, surgical team involved, weights of tissue removed, estimated blood loss, drain outputs in the immediate postoperative period, date that drain(s) were removed) and complications within 30 days of the index operation including hematoma requiring operative washout or bedside evacuation, seroma, cellulitis, nipple-areolar complex necrosis, fat necrosis, delayed wound healing, deep vein thrombosis and pulmonary embolism. Patients with insufficient records or those who are lost to follow-up will be excluded from the final analysis.

b) Statistical Analysis

[figure not shown]
We have partnered with our institution's Department of Surgery faculty biostatisticians on the statistical methods for this proposal. **Based on a Bayesian approach, a sample size of 100 patients will be sufficient to adequately power this study.**

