The primary objective of this pilot study is to explore whether, and to what extent, treatment using TXA decreases the risk of hematoma in patients undergoing breast reduction mammoplasty (BRM) compared to a saline placebo. A double-blind within-subjects design will be used with each patient receiving both treatments and thus serving as their own control. A simple randomization scheme will determine which treatment will be used for each side (left or right) for each patient. A Bayesian approach will be employed to estimate the posterior probability distribution of the

relative risk reduction in post-surgical hematoma between treatment rate between treatment with TXA and control. This posterior probability distribution provides the information necessary to answer the salient questions informative about the presence and strength of an efficacy signal for TXA; specifically, what is the probability that treatment with TXA reduces the risk of hematoma, compared to control by an amount δ for any $0 < \delta < 1$. Note that the probability that the relative risk < 1 corresponds to the probability that treatment with TXA is superior to the control. A description of this approach follows.

Prior to data collection and consistent with a null hypothesis of no difference between treatments we assume that the effect of treatment with TXA is equal to the effect of treatment with control. This assumption is formalized by assuming that the probability of developing a hematoma is the same for each treatment. The Bayesian approach considers this prior probability of developing a hematoma to be a random variable, which we specify to be a beta distribution with parameters 0.35 and 4.65, translating into a mean of 0.07 (the assumed hematoma rate for both treatments under the “null” hypothesis) and a standard deviation of about 0.10. Since patients will be treated with both treatments, the prior probabilities of developing a hematoma are not assumed to be independent. In our approach, we assume a conservative correlation of 0.30.

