Secondary endpoints will be analyzed using classical frequentist methods, with generalized linear models used to assess treatment group difference in blood transfusion, incidence of deep vein thrombosis, and incidence of thromboembolic events.

9. Data Safety Monitoring Plan

There will be regularly scheduled monitoring reviews at 6-month time intervals to review rates of adverse events, which will determine if the study poses sufficiently low risk to proceed. The DSMB will be comprised of two members of the Department of Surgery who are not affiliated with the study ([name], MD and [name], MD), as well as a biostatistician from the Albert Einstein College of Medicine/Montefiore Medical Center ([name], DrPH). The incidence of venous thromboembolism (VTE) in reduction mammoplasty ranges from 0.22% to 2.9%. A recent National Surgical Quality Improvement Program study describes a 0.17% rate of pulmonary embolism and a 0.07% rate of deep vein thrombosis in BRM patients.¹⁸ Furthermore, the incidence of seizure in the general population is estimated at 3%.¹⁹ With an anticipated sample size of 100 patients, if more than 2 patients (1.5%) develop either a deep vein thrombosis, pulmonary embolism, or seizure postoperatively, the study will be paused while further investigation regarding safety takes place. In the case of increased incidence of adverse events that warrant further investigation, the study will be paused and the PSF grant office will be kept apprised. We do not anticipate increased risk for thromboembolic events or seizure, given the well-described safety profile of tranexamic acid even in hypercoagulable populations such as bedbound or cancer patients, and given that we are using a low, topical dosage with fractional systemic absorption.

Although creation of the data-set will require use of patient names and medical record numbers, these will be stripped as soon as data-collection is complete and a linking file will be kept under lock and key by the primary investigator. The data set will be stored on Montefiore's encrypted server. Only the study team will have access to the

stored data, and only the study team will have access to the linking file. Data will be stored until the data is analyzed and scholarly output is generated. All members of the research team have undergone appropriate Human Subjects Protection training.

10. References

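### The secondary analysis compares treatment groups on transfusion, DVT and thromboembolism, but every patient receives both treatments, so the randomised data contain no such comparison

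*Combined protocol and SAP*

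**What the plan says.** The design is within-patient. Section 7 states: "Patients will be randomized to receive topical tranexamic acid to one breast and placebo (topical saline) to the other". Section 8(b) confirms it: "A double-blind within-subjects design will be used with each patient receiving both treatments and thus serving as their own control". Only the side is randomised, and section 3(c) excludes unilateral reductions, so no enrolled patient is planned to receive saline alone.

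The secondary outcomes in section 3(d) are transfusion within 30 days, deep vein thrombosis (DVT) and pulmonary embolism (PE). No section gives a rule for assigning such an event to a breast. For their analysis, the end of section 8(b) specifies "generalized linear models used to assess treatment group difference in blood transfusion, incidence of deep vein thrombosis, and incidence of thromboembolic events".

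The hypotheses do not all point to the same comparison:

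- Section 3(a) expects TXA to "decrease the rate of hematoma formation and the rate of blood transfusion without increasing the incidence of deep vein thrombosis or thromboembolic events", and names no comparator for the patient-level events.
- Section 8 opens with a similar statement, that TXA "will decrease total perioperative blood loss, hematoma formation, and transfusion rates without increasing the incidence of deep vein thrombosis or thromboembolic events".
- Section 3(d) uses an external comparator, for thromboembolic events only: treated patients "will not have an increased rate of thromboembolic events compared to nationally published rates and those of our own historical controls".

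The complications listed for abstraction in section 8(a) are "hematoma requiring operative washout or bedside evacuation, seroma, cellulitis, nipple-areolar complex necrosis, fat necrosis, delayed wound healing, deep vein thrombosis and pulmonary embolism". Transfusion is not among them.

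**The concern.** A treatment-group model needs some units with TXA and some without. For hematoma the unit is the breast, and the contrast exists. Transfusion, DVT and PE follow an operation in which the patient received both syringes, so for these outcomes the whole trial is one exposed cohort.

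Two consequences follow. First, the thromboembolic hypothesis is one of no increase, and an analysis that can only return no difference would appear to confirm it. A reader of a double-blind randomised trial could take that as randomised safety evidence. Second, the hypothesised fall in transfusion has no comparison behind it, because no section names a comparator, internal or external.

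**Working it through.** The plan gives no power, alpha or margin for the secondary endpoints, so there is no stated figure to reproduce. The check has two parts: whether the planned contrast exists, and what the data could support instead.

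**Inputs.** n = 100 patients (sections 8(b) and 9), all exposed to TXA (sections 7 and 8(b)). Background venous thromboembolism (VTE) rate 0.22% to 2.9%, PE 0.17%, DVT 0.07% (section 9). Adding the last two gives 0.17% + 0.07% = 0.24%, assuming no patient has both.

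**1. Patient-level model.** logit P(event) = a + b × TXA, with TXA = 1 for all 100 patients. The two columns of the design matrix are identical, so its rank is 1 of 2 and b cannot be estimated. More patients would not change this.

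**2. Breast-level model with the patient's event copied to both sides.** The plan does not say it would do this; it is the only way to give the model two groups within the trial. With x events, both groups have x/100, so log OR = 0 for any x. For illustration, x = 3 (an assumed count):

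- SE = √(2/3 + 2/97) = 0.829
- OR = exp(0) = 1.00, p = 1.00
- naive 95% CI = exp(±1.96 × 0.829) = 0.20 to 5.08

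Every pair is concordant, so a conditional model has no information at all.

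**3. What one cohort of 100 can show.** For 0 events the exact (Clopper-Pearson) two-sided 95% upper limit is 1 − 0.025^(1/100) = 3.62%. For 1, 2 and 3 events the upper limits are 5.45%, 7.04% and 8.52%. Against the cited rates:

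| Benchmark | Expected events in 100 | P(0 events) = (1 − p)^100 | 3.62% ÷ benchmark |
|---|---|---|---|
| 0.22% | 0.22 | 80% | 16.5 |
| 0.24% | 0.24 | 79% | 15.1 |
| 2.9% | 2.9 | 5% | 1.25 |

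**4. Sensitivity of the external comparison.** The one-sided 2.5% level and the doubling are assumptions made here, because the plan sets neither.

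- Against 0.24%, an exact binomial test rejects at 2 or more events (size 0.024). Its power at a true 0.48% is 8%.
- Against 2.9%, it rejects at 8 or more events (size 0.009). Its power at a true 5.8% is 22%.

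The second figure is partly an effect of discreteness: rejecting at 7 or more events has size 0.027 and power 36%.

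**5. Dependence on the benchmark.** Two events would reject 0.24% (p = 0.024), yet two is fewer than the 2.9 expected at 2.9%. The same result reads as harm or as reassurance according to which cited rate is used.

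**The case against.** The strongest reply is that the models were meant to compare trial patients with historical controls. Section 3(d) names such controls for thromboembolic events, section 3(e) calls the prospective patients a treatment arm, and section 4(a) excludes patients from before electronic records, a limit that makes most sense for retrospective patients. A binomial model with a cohort indicator would be estimable. On that reading the defect is an unnamed comparator, and deleting the models goes too far.

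This is a possible reading, but section 8(b) does not state it, and in that section treatments means TXA and control within a patient. It would still leave dates, cohort size and adjustment unspecified, and transfusion without a comparator. What stands is that a historical comparison is legitimate if it is specified and labelled as non-randomised. The fix allows for that.

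Other points have partial force:

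- The plan nowhere says it would copy events to both breasts, so the odds ratio of 1.00 is an illustration. The patient-level result does not depend on it.
- The power figures rest on a level and an effect chosen for this check, and this is described as a pilot. They show how weak the external comparison is; the main point does not need them.
- The abstraction list is introduced as inclusive, so the missing transfusion field may be only an omission in wording.
- A transfusion prompted by a one-sided hematoma could in principle be assigned to a breast. No rule for this exists, and none is plausible for DVT or PE.

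**Conclusion.** The concern holds, and it should be fixed before analysis. As written, the secondary models have no TXA-versus-control contrast for transfusion, DVT or thromboembolic events, and no choice of generalized linear model recovers one from the randomised data. This follows from the design and rests on one premise: these outcomes are recorded per patient, with no rule linking them to a breast.

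The external comparison that remains is non-randomised. With 0 events it excludes rates above 3.6%. That rules out only large increases over the low end of the cited range, and it leaves rates up to 1.25 times the high end compatible with the data.

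The damage is confined to the secondary claims. The primary hematoma endpoint is breast-level and keeps its paired comparison. The pause rule in section 9 uses a pooled patient count and does not depend on the contrast.

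**What to change.** 1. In section 8(b), delete the treatment-group generalized linear models for these endpoints. Report transfusion, DVT and PE as per-patient incidence in a single TXA-exposed cohort, with exact 95% intervals.
2. Reconcile this with section 3(d). Set the thromboembolic results beside both ends of the cited range (0.22% and 2.9%) and the 0.17% PE and 0.07% DVT rates. Fix these benchmarks in advance and label the comparison descriptive and non-randomised.
3. If historical controls are used, state their source, period and any adjustment, and name the model as a trial-versus-historical comparison.
4. Reword the hypotheses in sections 3(a) and 8 so that transfusion is descriptive and the claim of no increase in thromboembolic events refers only to the external comparison.
5. Add transfusion within 30 days to the abstraction list in section 8(a).

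Optional and exploratory: if drain output is recorded by side, a paired TXA-minus-control analysis would give the blood-loss hypothesis in section 8 a randomised comparison. Section 3 of the plan's argument, under Significance, itself treats the clinical meaning of drain output as uncertain.

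The cost is protocol and SAP wording plus one data field. Randomisation, sample size and the primary analysis do not change. The trial gives up a randomised transfusion and safety comparison that its design could never provide.

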Although creation of the data-set will require use of patient names and medical record numbers, these will be stripped as soon as data-collection is complete and a linking file will be kept under lock and key by the primary investigator. The data set will be stored on Montefiore's encrypted server. Only the study team will have access to the stored data, and only the study team will have access to the linking file. Data will be stored until the data is analyzed and scholarly output is generated. All members of the research team have undergone appropriate Human Subjects Protection training.

c) Provisions to Monitor the Data to Ensure the Safety of Subjects/Data Safety and Monitoring Plan

There will be regularly scheduled monitoring reviews by a Data Safety Monitoring Board (DSMB) at 6-month time intervals to review rates of adverse events, which will determine if the study poses sufficiently low risk to proceed. The DSMB will be comprised of two members of the Department of Surgery who are not affiliated with the study ([name], MD and [name], MD), as well as a biostatistician from the Albert Einstein College of Medicine/Montefiore Medical Center ([name], DrPH). The incidence of venous thromboembolism (VTE) in reduction mammoplasty ranges from 0.22% to 2.9%. A recent National Surgical Quality Improvement Program study describes a 0.17% rate of pulmonary embolism and a 0.07% rate of deep vein thrombosis in BRM patients.¹⁸ Furthermore, the incidence of seizure in the general population is estimated at 3%.¹⁹ With an anticipated sample size of 100 patients, if more than 2 patients (1.5%) develop either a deep vein thrombosis, pulmonary embolism, or seizure postoperatively, the study will be paused while further investigation regarding safety takes place. In the case of increased incidence of adverse events that warrant further investigation, the study will be paused and the PSF grant office will be kept apprised. We do not anticipate increased risk for thromboembolic events or seizure, given the well-described safety profile of tranexamic acid even in hypercoagulable populations such as bedbound or cancer patients, and given that we are using a low, topical dosage with fractional systemic absorption.

d) Provisions to Protect the Privacy Interests of Subjects

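### The only numerical safety trigger is a fixed count of events, tied neither to the number of patients treated nor to any one of the background rates the plan quotes

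*Combined protocol and SAP*

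**What the plan says.** Sections 5c and 9 (Data Safety Monitoring Plan) carry the same rule. It opens "With an anticipated sample size of 100 patients" and continues "if more than 2 patients (1.5%) develop either a deep vein thrombosis, pulmonary embolism, or seizure postoperatively, the study will be paused". No number treated, interim denominator or probability of pausing is attached to it.

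Three background figures stand just before the rule. One is a VTE range for reduction mammoplasty of 0.22% to 2.9%. The second is a national surgical database study that "describes a 0.17% rate of pulmonary embolism and a 0.07% rate of deep vein thrombosis in BRM patients". The third is a general-population seizure figure of 3%, given without a time window. The plan does not say which of these the count was set against.

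The same sections provide two unquantified safeguards: DSMB reviews of adverse event rates every six months, which decide whether the study may proceed, and a pause if an increased incidence of adverse events warrants investigation. Section 3e expects data collection to take 8 months.

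Under sections 3a and 7 every patient receives tranexamic acid in one breast. For thromboembolic safety, section 3d hypothesises that treated patients "will not have an increased rate of thromboembolic events compared to nationally published rates" and those of the institution's own historical controls.

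**The concern.** DVT, PE and seizure are systemic events, so the contralateral breast cannot serve as a control for them. With no untreated patients, safety monitoring has to compare a count with an external rate. The plan quotes several external rates that differ more than ten-fold and ties its trigger to none of them. It also applies the same count after 10 patients as after 100.

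A count that is not calibrated to a rate can fail in either direction. If the true background is near the low figures, the rule is insensitive and two early events pass under it. If the background is near the high figures, the rule is more likely than not to pause a trial in which the drug does no harm. The DSMB cannot tell from the text which of these it is working with.

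**Working it through.** **The plan's own percentage.** Two of 100 is 2.0% and three of 100 is 3.0%, so neither reading of the count gives the bracketed 1.5%. That figure equals 3/200, which would be a denominator of breasts although the events belong to patients. Taken as a limit on 100 patients it means 1.5 patients, so a pause at two events. The main calculation uses the words: more than 2, that is, 3 or more.

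**Inputs**
- Trigger: X ≥ 3 among n = 100 (sections 5c and 9).
- Low VTE background: 0.17% + 0.07% = 0.24% (sections 5c and 9), assuming that no patient has both. The lower end of the quoted range, 0.22%, is close to it.
- High VTE background: 2.9% (same sections).
- Seizure: 3% (same sections), or 0.1% without and 0.7% with tranexamic acid in the cardiac surgery trial cited in section 4c.
- Five-fold and ten-fold rises are illustrative choices. The documents name no rise to be detected.

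**Formula.** With independent patients and all 100 followed, P(pause) = 1 − P(0) − P(1) − P(2), where P(k) = C(100,k) p^k (1−p)^(100−k).

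At p = 0.024 (ten times 0.24%): 1 − 0.0881 − 0.2166 − 0.2637 = 0.432.
At p = 0.012 (five times 0.24%): 1 − 0.2990 − 0.3632 − 0.2183 = 0.12.
At p = 0.029: 1 − 0.0527 − 0.1574 − 0.2327 = 0.557.

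| Background taken from the plan | No increase | VTE five-fold | VTE ten-fold |
|---|---|---|---|
| VTE 0.22%, no seizures | 0.15% | 9.9% | 37.8% |
| VTE 0.24%, no seizures | 0.2% | 12% | 43% |
| VTE 0.24% + seizure 0.1% | 0.5% | 14% | 46% |
| VTE 0.24% + seizure 0.7% | 6.9% | 30% | 60% |
| VTE 0.24% + seizure 3% | 63% | 80% | 91% |
| VTE 2.9%, no seizures | 56% | about 100% | about 100% |

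Rates are added, which assumes that no patient has more than one type of event.

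**Early events.** At 0.24%, P(X ≥ 2 in 20) = 1 − 0.9531 − 0.0459 = 0.001, yet two events leave the count untriggered. At 2.9% the same probability is 0.113, so two in 20 would be unremarkable. Whether an early pair is a signal depends on the reference rate that the plan leaves open.

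**Does the missing denominator drive the low sensitivity?** As an arithmetic probe only, and not a proposed rule, an extra pause at two events in the first 25 patients was added. At 0.24%, detection moves from 12.0% to 13.3% (five-fold) and from 43.2% to 44.8% (ten-fold). An early-only adjustment changes little. The low sensitivity comes mainly from a rare event, 100 patients and the final count.

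**If the 1.5% is the intended limit** (X ≥ 2 of 100), at 0.24% the rule pauses 2.4% of trials with no increase, 34% at five-fold and 70% at ten-fold.

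**The case against.** A reader might infer that the rule simply misses a five- to ten-fold rise on the plan's VTE rate. The documents do not support that as a general statement. The figure of 0.24% is one of several that the plan quotes. A rise is missed more than half the time only for backgrounds up to about 0.53% (five-fold) or 0.27% (ten-fold), and at 2.9% the problem reverses into frequent pauses without harm. The rule also counts seizures. With the 0.7% figure added, a ten-fold VTE rise is caught 60% of the time. Even on 0.24% alone, the ten-fold result (43% paused, 57% missed) is not far from even. All of this stands, and it is why the point concerns calibration and not low sensitivity alone.

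A reader might also infer that an early cluster would be ignored. Three events pause the study at any time, however few patients have been treated. Two events could be acted on by the DSMB, which includes a biostatistician and reviews rates, or under the discretionary pause. That too stands. These safeguards are weak, however. They have no number or reference rate, and if the 8-month timeline holds and the review clock starts with data collection, only one scheduled six-monthly review falls within it.

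Finally, section 8b describes the trial as a pilot. The plan claims no detection power for the rule and nowhere says that completing without a pause would demonstrate safety. That inference should not be attributed to it.

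**Conclusion.** The concern holds in this form: the count is tied neither to the number treated nor to a reference rate, and no operating characteristics are stated. With no added harm, the chance of a pause runs from about 0.2% to 56% across the plan's own VTE rates, and is 63% if the 3% seizure figure is added to 0.24% VTE. A rule with that spread is not calibrated to any of the quoted figures. If 0.24% is meant, it pauses 12% of trials at a five-fold rise and 43% at a ten-fold rise. These results assume independent patients, complete follow-up of 100, events counted once per patient and additive rates. The multiples are illustrative.

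This should be corrected because it bears on patient safety and costs little. It is not a finding that patients are unprotected, since the DSMB keeps discretion to act.

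**What to change.** In sections 5c and 9, reconcile the trigger with the rates quoted beside it:

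1. Name one reference rate for the full composite of DVT, PE and seizure, with its time window, and say which quoted figures it comes from.
2. Have the DSMB statistician restate the trigger as events out of patients treated so far, in a short cumulative table covering the whole trial and not only its early part.
3. State the chance of pausing at the reference rate and at stated multiples of it.
4. Make the count and its bracketed percentage agree.

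The threshold itself is for the DSMB and clinicians to set, and none is proposed here.

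The cost is a short binomial calculation and a wording change in two sections, with no extra patients or procedures. The small downside is a somewhat higher, but stated, chance of a pause that proves unnecessary.
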